20.0 Provisions to Protect Participant Privacy and Data

Confidentiality:

All experimental procedures will be conducted in the Hearing Aid Lab at Northwestern University. The data for this study will include audiometric thresholds, age, cognitive measures, speech intelligibility scores, hearing aid fitting data, and acoustic measurements. Participant responses recorded through the computer interface will be coded and will not contain any identifiable information. All data will be de-identified prior to analysis. De-identification will take place by assigning a particular code to all data pertaining to one subject. The link between the subject code and the subject name will be stored in a password-protected file on a HIPAA-approved server managed by Northwestern School of Communication computer support staff. This information will also be stored on the secure REDCap database. Participant identifiers will be stored electronically on REDCap in a separate instrument than the study data. REDCap will also be used to track study data. All research staff will receive appropriate Human Subjects protection training and training regarding confidentiality. Data are only accessible by the study staff via password-protected files. Discussion regarding subject confidentiality will also be included during regular lab meetings.

21.0 Data Monitoring Plan to Ensure the Safety of Participants:

All experimental procedures will be conducted in the Hearing Aid Lab and the virtual sound room at Northwestern University. The data for this study will include audiological data, age, cognitive measures, and speech intelligibility scores, hearing aid fitting data, and acoustic measurements. Participant responses recorded by the experimenter through the computer interface will be coded and

will not contain any identifiable information. Any audio-recording done for the purpose of scoring will also be de-identified and will be deleted at the end of the experiment. All data will be de-identified prior to analysis. De-identification will take place by assigning a particular code to all data pertaining to one subject. The same subject code will be used in the hearing aid programming software. The link between the subject code and the subject name will be stored in a password-protected file on a HIPAA-approved server managed by Northwestern School of Communication computer support staff. All research staff will receive appropriate Human Subjects protection training and training regarding confidentiality. Data are only accessible by the study staff via password-protected files. Discussion regarding subject confidentiality will also be included during regular lab meetings.

The proposed research uses a very low-risk intervention (i.e., hearing aids). The investigator(s) will be responsible for ensuring participants' safety at the time of experimentation. If the investigator(s) determine that participation in the study places a participant at an unacceptable risk, enrollment or study tasks will not proceed. The participants will use the laboratory hearing aids only for the duration of the experiment. Therefore, the use of the intervention will always be monitored by the experimenter. The co-investigator is responsible for making the ear impressions and completing the hearing aid fitting. All testing will be conducted by an investigator, the research study coordinator, or a research assistant. The research assistant will be supervised by an investigator or the research study coordinator. The investigators as well as the research study coordinator are trained and licensed audiologists and have several years of experience in conducting hearing assessments, hearing aid fitting, and research with adults and are therefore qualified for monitoring the study.

**Statistical Analysis Plan:**

Primary analyses will assess the main effects and interaction between hearing aid processing (WDRC and directionality) and working memory to determine if the effect of hearing aid processing on the percentage correct (speech intelligibility) is different based on working memory ability. Specifically, a linear mixed effect model will contain fixed effects for working memory, hearing aid processing, and their interaction. A random subject effect will account for repeated measures on a subject and allow for separation of between subject and within subject variance components. Models will also consider adjustment for degree of hearing loss (pure tone average at 0.5, 1, 2, 4 kHz) and age by including both in the model as fixed effects. Residual diagnostics will assess model assumptions and transformations of the outcome may be considered if appropriate. Descriptive statistics will summarize demographic and audiological characteristics of the study population.

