Hearing loss is prevalent in approximately 37 million adults over the age of 18 years in the United States [1]. Hearing aids are the typical rehabilitative approach for most individuals with permanent hearing loss. While there is evidence that hearing aid use significantly improves the quality of life [2-4], hearing aid adoption rates are as low as 30% [4,5], due to lack of perceived benefit in difficult listening environments [3]. If hearing loss is not treated adequately, it can lead to broader consequences including social isolation and depression [6,7]. Therefore, an individualized approach to hearing healthcare including selection of hearing aids and customization of settings to the listener's abilities and environment, is integral to adherence to treatment, social engagement, and listener satisfaction [8]. The central focus of this research proposal is to inform the choice of hearing aid settings based on individual variability.

Signal modifications caused by collective hearing aid processing and environmental conditions affect individual benefit from hearing aids. An important relationship that has heavily influenced audiology practice is the finding that listeners with lower working memory capacity are disadvantaged by hearing aid signal processing that substantially modifies the speech signal (such as fast-acting wide dynamic range compression, or WDRC [9,10]). In response to this finding, researchers and some hearing aid manufacturers have advocated for less aggressive signal modification (such as slow-acting WDRC, which gradually adjusts hearing aid gain) and others have suggested that measurement of working memory or other cognitive abilities should be part of the clinical hearing aid fitting process.

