We may enroll a small group (n=30) of listeners with normal hearing, defined as pure-tone thresholds of 25 dB HL or less at octave frequencies between 250 and 3000 Hz. This group may be enrolled for the purposes of test validation, or to study the effects of hearing loss on the outcome measures. With the exception of having normal hearing, those participants will follow the inclusion and exclusion criteria described above.

The study will not recruit special populations such as adults unable to consent/cognitively impaired, minors, prisoners, or other detained individuals.

4.0 Sample Size:

The study will recruit 120 participants over a 3-year period. Each experiment will recruit approximately 30 participants (additional 10 account for pilot testing and attrition) for a total of 3 experiments.

Sample size considerations were based on the primary analyses of a mixed effect model with fixed effects for WDRC, working memory, and the interaction.

Simulations were performed based on a range of effect sizes and estimates of between subject and within subject variances. Our sample size of 15 subjects per working memory (high vs low), will provide at least 80% power to detect reasonable effect sizes for all three effects. Specifically, we assumed a conservative subject variance estimate of 0.01 and a residual variance estimate of 0.01 from pilot data, marginal effects for working memory of 0.70 (high) and 0.53 (low), and marginal effects for WDRC of 0.75 (fast) and 0.48 (slow). In simulations assuming a two-sided type one error, we had adequate power to detect all three effects. In simulations assuming less conservative variance estimates, our sample size will provide adequate power to detect even smaller effect sizes. Specifically, we assumed a subject variance estimate of 0.008 and a residual variance estimate of 0.006, marginal effects for working memory of 0.38 (high) and 0.17 (low), and marginal effects for WDRC of 0.33 (fast) and 0.22 (slow). We anticipate a range of effect sizes and variance estimates for models within each level of directionality, and thus considered simulations from a range of assumptions.

5.0 Recruitment and Screening Methods:

Recruitment process:

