Due to the COVID-19 pandemic, participant research visits may be conducted remotely using Northwestern IT-approved (and HIPAA-approved) video conferencing or phone. The research staff will conduct these visits from a private room in their apartment and no one else will be present during the research study. The research staff may also conduct these virtual visits from the hearing aid lab or an office space. Participants will perform the remote testing from their respective places of residence/a quiet place of their convenience. The virtual visits will be conducted either through Zoom or Microsoft Teams or WebEx applications. The platform used will be determined by participant preference.

7.0 Multi-site Research (research that involves external collaborating institutions and individuals): N/A

8.0 International Research (where data collection will occur outside the United States and U.S. territories): N/A

9.0 Procedures Involved:

The proposed research will measure speech intelligibility and signal fidelity with a combination of hearing aid settings under a variety of spatial conditions (Aim 1: ideal; Aim 2: realistic) for hearing-impaired listeners with different working memory capacities. The proposed research is a clinical trial and will use laboratory hearing aids to provide various combinations of hearing aid signal processing. Using a mixed design, individual variability in auditory and working memory capacity will be related to speech intelligibility and signal fidelity across test conditions. Test procedures including stimuli and outcome measures described below are common to both Aims 1 and 2.

Study tasks for all experiments will include the following steps per subject:

Session 1	Approx. Duration (2 hours)	Session 2	Approx. Duration (2 hours)	Session 3	Approx. Duration (2 hours)
Candidacy assessment	60-80 mins	Earmold + Hearing Aid Fitting	45-60 mins	Outcome measurement (Speech intelligibility testing, localization) continued	60-120 mins
Cognitive test*	15-30 mins	Outcome measurement (Speech intelligibility testing)	60 mins		
Earmold impression	15-20 mins				

*May include tests of working memory, executive function, and processing speed

Session 2 will take place ~10-15 days after session 1 to allow for time taken for the custom earmold order to be received. There is no minimum gap required between sessions 2 and 3. Session 3 may not be required for all experiments or participants.

Stimuli:

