flanker task, participants see a > or < sign, surrounded by two > or < signs on either side (e.g., >>>>, <<><>). Their task is to focus on the middle sign and decide whether that sign is pointing to the left or the right as quickly and as accurately as possible by pressing one of the two buttons (left or right). The reaction time difference between the compatible (e.g., >>>>) and incompatible stimuli (e.g., <<><>) will be used to index interference control ability. In the letter flanker task, participants will see either a letter G or H in the middle, surrounded by two Gs or Hs on either side (e.g., HHHHH, GGHGG).

Participants' task is to focus on the middle letter and determine as quickly and as accurately as possible whether it is a G or an H. Again, the reaction time difference between the compatible (e.g., HHHHH) and incompatible (GGHGG) stimuli will be used as the index of interference control ability.

Processing speed: This is the rate at which information is treated in the cognitive system. Individuals with higher processing speed are expected to have better outcomes especially when the conditions are more challenging.

WAIS-III Coding/Symbol Search [24] (3 minutes): Participants are presented with a series of letters and a key at the top of the page with a corresponding number. Below each letter is a space to write the corresponding number, and participants are asked to fill in as many of the numbers as they can within a certain amount of time.

Rationale for including additional cognitive measures: The above-described measures including AVDAT, measures of executive function, and processing speed may be included to explain variability in outcomes that may not be captured by the reading span test.

Peripheral auditory abilities: Participants may be asked to listen to tones, sounds of different frequencies and modulation, or noises of different lengths to determine auditory abilities beyond simple hearing thresholds. These measures are quick, non-invasive, and are presented at safe listening levels (i.e., 65-75 dB SPL) and pose little to no physical risk to participants. These sounds will be presented over headphones or speakers in a sound-treated room and may take 30 minutes to complete.

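### If the primary model pools WDRC and directionality with only a random subject intercept, the working-memory-by-WDRC test uses the wrong error term, and its type I error can move either way

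*SAP*

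**What the plan says.** The SAP's primary analysis addresses the "main effects and interaction between hearing aid processing (WDRC and directionality) and working memory". The outcome is percentage correct. The model has fixed effects for working memory, processing and their interaction, and "A random subject effect will account for repeated measures on a subject". The text mentions two variance components only, between subject and within subject. The natural reading is a random intercept, with no subject-specific response to WDRC or directionality.

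Protocol section 4.0 (Sample Size) describes a different structure. Its model contains WDRC, working memory and their interaction, with no directionality term, and it anticipates a range of effects and variances for "models within each level of directionality". On variance, "we assumed a conservative subject variance estimate of 0.01 and a residual variance estimate of 0.01 from pilot data". No variance is given for subjects' response to processing.

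Section 9.0 says the study "will use laboratory hearing aids to provide various combinations of hearing aid signal processing". Its session table schedules speech testing in session 2 and, where session 3 is needed, "Outcome measurement (Speech intelligibility testing, localization) continued". The Stimuli text allows several babble levels. Neither document says how many scores a subject contributes per setting, whether scores are averaged, or whether babble level varies within a subject.

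**The concern.** The working-memory-by-WDRC interaction asks whether the fast-minus-slow difference is larger at one level of working memory than at the other. Each subject supplies one such difference, so the proper yardstick is how much these differences vary between subjects at the same working-memory level. A random intercept removes a subject's overall level but not the subject's own response to WDRC. Once a subject gives two or more scores per WDRC setting, as in any model that crosses WDRC with directionality, the intercept-only model estimates its error from a residual that mixes several sources. That residual matches the required variance only by coincidence, or if responses do not vary.

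The protocol gives some reason to expect varying responses. Section 2.0 states: "The central focus of this research proposal is to inform the choice of hearing aid settings based on individual variability". Section 9.0 adds cognitive measures that "may be included to explain variability in outcomes that may not be captured by the reading span test". Neither statement supplies an SD.

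This interaction is the primary question, and it is meant to inform whether working memory should be measured in routine hearing aid fitting. A miscalibrated test would overstate or understate that evidence. The SAP's residual diagnostics do not replace the error term.

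**Working it through.** **Inputs from Protocol 4.0.** 15 subjects per working-memory group; residual variance e = 0.01 (second scenario 0.006); subject variance 0.01 (second scenario 0.008). Two-sided testing is stated.

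**Assumed, because the documents do not give them.** A 5% level; two directionality levels; SDs of subjects' true differences within a working-memory group, sW (fast minus slow) and sD (directional minus omnidirectional), of 0.05, 0.07 and 0.10; scores per cell; noise levels.

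**The plan's own figure first (at least 80% power for three effects).** Within one directionality level and one score per WDRC setting:
- Working memory, first scenario: SD = sqrt(0.01 + 0.01/2) = 0.1225; SE = 0.1225 x sqrt(2/15) = 0.0447; power for 0.70 - 0.53 = 0.17 is 0.967 (0.956 by noncentral t).
- WDRC, 0.75 - 0.48 = 0.27: SE = sqrt(2 x 0.01/30) = 0.0258; power above 0.999.
- In the second scenario both exceed 0.999.
- Interaction: no size is stated, so its power cannot be reproduced. SE = sqrt(2 x 0.01) x sqrt(2/15) = 0.0516, so 80% power needs a difference in differences of about 0.145 (0.112 in the second scenario).

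**Error term, pooled 2x2, one score per cell.** A subject's fast-minus-slow contrast, averaged over directionality, has variance e + sW^2. The intercept-only model pools three within-subject components (WDRC, directionality, and their product), with expected mean squares e + sW^2, e + sD^2 and e. It therefore uses e + (sW^2 + sD^2)/3.

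Ratio of true to used error: R = (e + sW^2) / (e + (sW^2 + sD^2)/3). R > 1 exactly when 2sW^2 > sD^2. Approximate type I error = 2 x (1 - Phi(1.96/sqrt(R))).

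| sW | sD | True | Used | R | Type I error |
|---|---|---|---|---|---|
| 0.05 | 0 | 0.0125 | 0.01083 | 1.154 | 6.8% |
| 0.07 | 0 | 0.0149 | 0.01163 | 1.281 | 8.3% |
| 0.10 | 0 | 0.0200 | 0.01333 | 1.500 | 11.0% |
| 0.05 | 0.05 | 0.0125 | 0.01167 | 1.071 | 5.8% |
| 0.07 | 0.07 | 0.0149 | 0.01327 | 1.123 | 6.4% |
| 0.10 | 0.10 | 0.0200 | 0.01667 | 1.200 | 7.4% |
| 0.07 | 0.10 | 0.0149 | 0.01497 | 0.996 | 4.9% |
| 0.05 | 0.10 | 0.0125 | 0.01417 | 0.882 | 3.7% |

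Simulation (20,000 or more trials per case) agrees: 6.8/8.3/10.6% if only WDRC response varies, 5.9/6.4/7.3% if both vary equally, 5.0% at 0.07 and 0.10, and 3.7% at 0.05 and 0.10. REML random-intercept fits gave 10.4% (sW = 0.10 only, 500 fits) and 6.5% (both 0.10, 400 fits). With e = 0.006 the simulated figures are 7.6/10.2/13.3% and 6.3/7.0/8.1%, and 3.2% at 0.05 and 0.10.

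**Within one directionality level, one score per WDRC setting.** The required variance of a difference is 2e + sW^2. The intercept model's residual is e + sW^2/2, which implies the same 2e + sW^2. The test is valid; simulation gave 4.9-5.1%.

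**Two unaveraged scores per cell at one noise level, pooled.** R = (e + 2sW^2) / (e + 2(sW^2 + sD^2)/7). At sW = 0.10, sD = 0: 0.03/0.01286 = 2.33, or 19.9%. Simulation gave 9.9/13.6/19.5% (only WDRC varies) and 8.7/11.6/15.9% (both equal).

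**Noise effect left out.** With three noise levels at assumed means 0.4/0.6/0.8, unaveraged and with no noise term, the noise variance inflates the residual and type I error falls to 0.3/1.2/4.1% (only WDRC varies) or 0.2/1.1/3.7% (both equal).

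**Averaging alone is not a cure in the pooled model.** Averaging three scores per cell first and keeping the intercept only gives 9.9/12.4/16.4% and 7.0/8.0/8.9%.

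**Comparator.** A two-sample t test (28 df) on per-subject contrasts stayed at about 5% throughout (4.7-5.4%).

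**The case against.** The strongest reply is that the pooled model may not be the one intended. Section 4.0 bases the sample size on a WDRC-by-working-memory model and speaks of separate models by directionality level. The SAP also uses the plural when it discusses covariate adjustment, and it never says outright that the two processing factors are crossed. With one score per WDRC setting the by-level analysis is valid. This stands: whether there is a problem depends on which document governs, and the two must be reconciled.

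Second, a reader might infer that the pooled test is liberal whenever subjects differ in their response. It is not. If directionality response varies enough more than WDRC response, the test is conservative, and nothing in the documents says which varies more.

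Third, the evidence for varying responses is indirect. The remark about extra cognitive tests concerns variability in outcomes, not in response to processing, and part of the individual variability in section 2.0 is working memory itself, already a fixed effect. This also stands; all response SDs here are assumptions.

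Fourth, the session times might be read as showing several scores per cell, and hence errors near 20%. They do not establish this: session 3 may not be needed and includes localization, and the time is also shared among spatial conditions.

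Fifth, if the primary test is a joint 3-df test of working memory by processing, the distortion is smaller: 4.9-6.3% with one score per cell where only WDRC response varies or both vary equally. The SAP does not say whether the test is joint or by component.

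What remains is that the model as the SAP reads has no term for subject-specific response, and its test of the WDRC component is calibrated only by coincidence or if responses do not vary.

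**Conclusion.** The concern holds conditionally. If the primary analysis pools directionality as the SAP reads, the intercept-only error term for working memory by WDRC is wrong whenever responses vary, except at 2sW^2 = sD^2. With one score per cell, first-scenario variances and SDs of 0.05 to 0.10, type I error runs from about 4% to 11% against a nominal 5%. It is about 10-20% (only WDRC varies) or 9-16% (both equal) if two unaveraged scores per cell enter at one noise level, and well below 5% if a large noise effect is omitted. These last figures illustrate what an unstated design could produce; they are not estimates for this trial.

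A reader might also infer a shortfall against the stated 80% power. The documents do not support that: both main effects exceed it comfortably, and no interaction size is given to test. The point merits a change because it concerns the primary test and the cure is cheap. Confidence is medium, since the response SDs and the layout of scores are not documented.

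**What to change.** In the SAP:

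1. Reconcile it with Protocol 4.0 by stating whether the primary model pools directionality or is fitted within each level. State the number of scores per subject per setting, whether they are averaged, and whether noise level varies within subject in each experiment.
2. Wherever a subject gives more than one score per WDRC or directionality setting, including any pooled model, test working memory by WDRC and working memory by directionality on per-subject contrasts. The equivalent is by-subject slopes for both factors with Kenward-Roger or Satterthwaite degrees of freedom; use the slopes version where a subject has incomplete cells, since the protocol allows data from withdrawn participants to be used.
3. If noise level varies within subject, include it as a within-subject factor or average over it, in either case together with item 2.

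With one score (or one averaged score) per WDRC setting within one directionality level, the random intercept suffices and no slope can be estimated.

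The cost is SAP wording only, with no new data. The interaction would have about 28 degrees of freedom. If subjects' responses truly do not differ, power in the pooled 2x2 with one score per cell is about 78% instead of 80% at an interaction of 0.103.

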Recorded speech materials (words, sentences, or passages) will be presented. These speech materials will be combined with multi-talker babble at varying levels (including no noise), and the intensity of the stimuli will be adjusted to represent typical conversational speech (65 dB SPL).

The listener will be fit with hearing aids that are either commercially available or an open-platform hearing aid or a computer simulation of a hearing aid [e.g., 9] that allows flexible adjustments compared to commercial hearing aids and ensures adequate scientific rigor. The hearing aids will be fit to a foam/ear tip or a custom earmold and the amplification levels will be set appropriate to the individual's hearing. If a computer simulation is used, the amplified/processed sounds will be presented via headphones or earphones and the amplification levels will be set appropriate to the individual's hearing.

Earmold impression: First, the ear is visually inspected with an otoscope (lighted magnifying scope). Then a cotton/foam block and soft impression material are placed in the ear. The material is left to set for about 3 mins after which it is removed along with the cotton/foam block and is used to order an earmold for later testing. This is a standard clinical procedure.

Loudness discomfort levels: Participants will be played sounds at progressively louder levels and asked to verbally indicate the maximum point of listening comfort. Loudness discomfort levels will be measured at 0.5 and 3 kHz and used in combination with patient report. This is a standard clinical test used to verify that stimuli levels are not uncomfortably loud.

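### Does the SAP's permission to transform percentage correct after residual checks leave the primary interaction without a defined scale?

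*SAP*

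**What the plan says.** The SAP's single paragraph sets the primary question as "to determine if the effect of hearing aid processing on the percentage correct (speech intelligibility) is different based on working memory ability". The model is also stated: "a linear mixed effect model will contain fixed effects for working memory, hearing aid processing, and their interaction", with a random subject effect. After the covariates it adds: "Residual diagnostics will assess model assumptions and transformations of the outcome may be considered if appropriate". No transformation, diagnostic threshold or back-transformation is named.

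Protocol section 4.0 (Sample Size) works only in proportions. One scenario takes "marginal effects for working memory of 0.70 (high) and 0.53 (low), and marginal effects for WDRC of 0.75 (fast) and 0.48 (slow"), with subject and residual variances of 0.01 each. The other takes "a subject variance estimate of 0.008 and a residual variance estimate of 0.006, marginal effects for working memory of 0.38 (high) and 0.17 (low"), with WDRC means of 0.33 (fast) and 0.22 (slow). The claim is that "Our sample size of 15 subjects per working memory (high vs low), will provide at least 80% power to detect reasonable effect sizes", and it is made of both main effects and the interaction. Section 9.0 (Stimuli) says of the listening conditions: "These speech materials will be combined with multi-talker babble at varying levels (including no noise"), so scores near the floor or ceiling are possible.

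**The concern.** For a main effect, a monotone transformation mostly changes the fit. For an interaction it can change the hypothesis. If both main effects are non-zero, as section 4.0 assumes, equal fast-minus-slow gains in percentage points are unequal gains in log-odds, and the reverse. A scale chosen after the residuals are seen could therefore decide whether working memory is said to modify the effect of processing.

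The protocol's Background holds that "listeners with lower working memory capacity are disadvantaged by hearing aid signal processing that substantially modifies the speech signal". If that means a smaller gain from fast WDRC in low-memory listeners, then in the low-mean scenario it is the direction in which a move to log-odds loses power. The power statement, being in proportions, would also not carry over to a transformed outcome.

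**Working it through.** **Inputs.** Means and variances from protocol section 4.0; 15 listeners per working-memory group. Assumed, because not stated: two-sided alpha of 0.05 and one score per listener per WDRC setting. A positive interaction means that high-memory listeners gain more from fast over slow WDRC.

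**1. The plan's own power figure.**
- Working memory: SE = sqrt(2 × (subject variance + residual variance/2)/15). High-mean: sqrt(2 × 0.015/15) = 0.0447; 0.17/0.0447 = 3.80; power 95.6% (t, 28 df). Low-mean: sqrt(2 × 0.011/15) = 0.0383; 0.21/0.0383 = 5.48; power above 99.9%.
- WDRC: power above 99.9% in both scenarios.
- Interaction: SE = sqrt(4 × residual variance/15) = 0.052 (high-mean) and 0.040 (low-mean). The protocol gives no interaction size, so the 80% claim cannot be reproduced for this term. It would need about 15 points (high-mean) or 12 points (low-mean).

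**2. No interaction in percentage points, re-expressed in log-odds.** Each cell is the overall mean plus or minus half of each main effect.

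| Scenario | High fast / slow | Low fast / slow | Log-odds gain, high vs low | Interaction |
|---|---|---|---|---|
| Low-mean | 0.435 / 0.325 | 0.225 / 0.115 | 0.47 vs 0.80 | -0.33 |
| High-mean | 0.835 / 0.565 | 0.665 / 0.395 | 1.36 vs 1.11 | +0.25 |

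**3. The converse: same margins, no log-odds interaction.**
- Low-mean: (0.4490 - 0.3110) - (0.2110 - 0.1290) = +0.056, or +5.6 points. With SE 0.040 this is detected 27% of the time.
- High-mean: (0.8225 - 0.5775) - (0.6775 - 0.3825) = -0.050, or -5.0 points. With SE 0.052, 15%.

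**4. Power if every dataset were analysed in log-odds.** Simulation with normal errors, the stated variances and scores clipped just inside 0 and 1; the interaction is set before clipping.

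| Interaction set | Percentage correct | Logit |
|---|---|---|
| Low-mean, +10 points | 74% | 10-11% |
| Low-mean, -10 points | 55-56% | 93% |
| High-mean, +10 points | 39% | 78% |
| High-mean, -10 points | 52% | 7-8% |

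At zero interaction, percentage correct rejects 5.3-5.9%. Logit rejects 27-30% (low-mean) or 19-21% (high-mean), and arcsine 7.5-9.5%. The excess is not false positives: step 2 shows that those cells do have an interaction on the other scale.

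**5. Power if only poor residuals lead to a switch.** Assumed trigger: a Shapiro-Wilk test, or a rank correlation of absolute residual with fitted value, at p < 0.05.
- With normal errors and clipping, the trigger fires in 7-16% of datasets. Rejection at zero percentage-point interaction in the low-mean scenario goes from 5% to 10-11% with logit, or 7% with arcsine.
- Power changes with logit: low-mean +12 points, 84-85% to 77-78%; low-mean -12, 84% to 87%; high-mean -15, 81-82% to 77-78%; high-mean +15, 82-83% to 84%.
- With logit-normal effects and binomial scoring, the trigger fires far more often (20-65% across runs), rejection at zero reaches about 18%, and keeping percentage correct forgoes about 5-11 points of power where a switch would help.

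**6. Is there reason to look at residuals?** Yes. With total SD sqrt(0.02) = 0.141, a normal model puts 12% of high-memory fast scores above 1 (mean 0.835). With SD sqrt(0.014) = 0.118, it puts about 17% of low-memory slow scores below 0 (mean 0.115).

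**The case for a change.** The best case for a change is that it is cheap. One sentence fixing percentage correct as the deciding scale, and one named sensitivity model, would remove discretion from the primary test. Error control on percentage correct held at about 4-6% in every set of runs. Where a switch does occur, the two scales can give opposite answers, and Aims 1 and 2 cover listening conditions whose mean scores may differ, which makes a common scale more useful.

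The scale dependence stands, and so does the point that a rule would make the SAP tidier. The rest is weaker. The clause does not say that a transformed result replaces the named outcome. The null changes only if a switch is made and both main effects are non-zero; a crossover interaction keeps its direction on any monotone scale, and the Background statement could describe one. The predicted direction loses power from a switch in the low-mean scenario but gains in the high-mean one. Nor is percentage correct the only defensible choice: a statistician could equally name a binomial mixed model for a score with this much mass near its limits.

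**Conclusion.** No change is called for. The plan states its outcome, model and question, and no figure or rule in it is shown to be wrong. What is missing is the detail behind a permissive clause, and a competent analyst supplies it: keep percentage correct as the reference because the SAP names it, check floor and ceiling, and show any transformed model alongside with the interaction also expressed in percentage points.

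Barring a change of scale is a trade-off on which statisticians reasonably differ. It protects the stated hypothesis, but forgoes about 1 to 11 points of power where a switch would help and saves several points where it would hurt. The algebraic results (-0.33, +0.25, +5.6 and -5.0) need only the protocol's means. The simulated rates are illustrative, since the trigger, item count, transformation and noise model are assumed and the results move materially when the noise model changes.
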